#### 12.1.3 Protocol Amendment and/or Revision

Any changes to the study that arise after approval of the protocol must be documented as protocol amendments: substantial amendments and/or nonsubstantial amendments.

Depending on the nature of the amendment, either IRB/IEC, Competent Authority approval or notification may be required. The changes will become effective only after the approval of the sponsor, the investigator, the regulatory authority and the IRB/IEC (if applicable).

Amendments to this protocol must be signed by the sponsor and the investigator. Written verification of IRB/IEC approval will be obtained before any amendment is implemented which affects subject safety or the evaluation of safety, and/or efficacy. Modifications to the protocol that are administrative in nature do not require IRB/IEC approval, but will be submitted to the IRB/IEC for their information, if required by local regulations.

- CONFIDENTIAL -

If there are changes to the informed consent, written verification of IRB/IEC approval must be forwarded to the Sponsor. An approved copy of the new informed consent must also be forwarded to the Sponsor.

#### **12.1.4 Informed Consent of Subjects**

##### **12.1.4.1 Subject Information and Consent**

The investigator or his/her representative will explain the nature of the study to the subject or his/her guardian or legal representative, and answer all questions regarding this study. Prior to any study-related screening procedures being performed on the subject, the informed consent statement will be reviewed and signed and dated by the subject or his/her guardian or legal representative, the person who administered the informed consent and any other signatories according to local requirements. A copy of the signed ICF will be given to the subject and the original will be placed in the subject's medical record. An entry must also be made in the subject's dated source documents to confirm that informed consent was obtained prior to any study-related procedures and that the subject received a signed copy.

The signed consent forms will be retained by the investigator and made available (for review only) to the study monitor and auditor regulatory authorities and other applicable individuals upon request.

##### **12.1.4.2 Supply of New and Important Information Influencing the Subject's Consent and Revision of the Written Information**

1. The investigator or his/her representative will immediately inform the subject orally whenever new information becomes available that may be relevant to the subject's consent or may influence the subject's willingness to continue to participate in the study (e.g., report of serious drug adverse drug reaction). The communication must be documented in the subject's medical records and must document whether the subject is willing to remain in the study or not.
2. The investigator must update their ICF and submit it for approval to the IRB/IEC. The investigator or his/her representative must obtain written informed consent from the subject on all updated ICFs throughout their participation in the study. The investigator or his/her designee must reconsent subjects with the updated ICF even if relevant information was provided orally. The investigator or his/her representative who obtained the written informed consent and the subject should sign and date the ICF. A copy of the signed ICF will be given to the subject and the original will be placed in the subject's medical record. An entry must be made in the subject's records documenting the reconsent process.

#### **12.1.5 Source Documents**

Source data must be available at the site to document the existence of the study subjects and to substantiate the integrity of study data collected. Source data must include the original documents relating to the study, as well as the medical treatment and medical history of the subject.

- CONFIDENTIAL -

The investigator is responsible for ensuring the source data are attributable, legible, contemporaneous, original, accurate and complete whether the data are hand-written on paper or entered electronically. If source data are created (first entered), modified, maintained, achieved, retrieved or transmitted electronically via computerized systems (and/or other kind of electric devices) as part of regulated clinical trial activities, such systems must be compliant with all applicable laws and regulations governing use of electronic records and/or electronic signatures. Such systems may include, but are not limited to, electronic medical/health records, protocol related assessments, adverse event tracking, and/or drug accountability.

Paper records from electronic systems used in place of electronic format must be certified copies. A certified copy must be an exact copy and must have all the same attributes and information as the original. Certified copies must include signature and date of the individual completing the certification. Certified copies must be a complete and chronological set of study records (including notes, attachments, and audit trail information (if applicable). All printed records must be kept in the subject file and available for archive.

#### **12.1.6 Record Retention**

The investigator will archive all study data (e.g., subject identification code list, source data, eCRFs and investigator's file and relevant correspondence. These documents are to be kept on file for the appropriate term determined by local regulation (Five years after NDA approval). The sponsor will notify the site/investigator if the NDA is approved or if the IND is discontinued. The investigator agrees to obtain the sponsor's agreement prior to disposal, moving, or transferring of any study-related records. The sponsor will archive and retain all documents pertaining to the study according to local regulations.

Data generated by the methods described in the protocol will be recorded in the subjects' medical records and/or study progress notes. All data will be entered into the eCRFs.

#### **12.1.7 Subject Confidentiality and Privacy**

Individual subject medical information obtained as a result of this study is considered confidential and disclosure to third parties is prohibited. Such medical information may be given only after approval of the subject to the subject's physician or to other appropriate medical personnel responsible for the subject's well-being.

The sponsor shall not disclose any confidential information on subjects obtained during the performance of their duties in the clinical study without justifiable reasons.

All individuals and organizations involved in the study must pay very careful attention to protect subjects' privacy with appropriate measures, for example, by prohibiting the use of any private information that may identify a subject (e.g., name or address). These details shall be processed in accordance with the applicable local and regional laws.

Even though any individuals involved in the study, including the study monitors and auditors, may get to know matters related to subject's privacy due to direct access to source documents, or from other sources, they may not leak the content to third parties.

- CONFIDENTIAL -

The sponsor affirms the subject's right to protection against invasion of privacy. Only a subject identification number and/or initials will identify subject data retrieved by the sponsor. However, the sponsor requires the investigator to permit the sponsor, sponsor's representative(s), the IRB/IEC and when necessary, representatives of the regulatory health authorities to review and/or to copy any medical records relevant to the study.

The sponsor agrees to comply and process personal data in accordance with all applicable privacy laws and regulations, including, without limitation, the Personal Information Protection Law in Japan and Privacy laws in the US.

### **12.1.8 Arrangement for Use of Information and Publication of the Clinical Study**

Information concerning the study drug, patent applications, processes, unpublished scientific data, the Investigator's Brochure and other pertinent information is confidential and remains the property of the sponsor. Details should be disclosed only to the persons involved in the approval or conduct of the study. The investigator may use this information for the purpose of the study only. It is understood by the investigator that the sponsor will use the information obtained during the clinical study in connection with the development of the drug and therefore may disclose it as required to other clinical investigators or to regulatory agencies. In order to allow for the use of the information derived from this clinical study, the investigator understands that he/she has an obligation to provide the sponsor with all data obtained during the study.

Publication of the study results is discussed in the clinical study agreement.

### **12.1.9 Signatory Investigator for Clinical Study Report**

ICH E3 guidelines recommend that a final study report which forms part of a marketing authorization application be signed by the representative for the coordinating investigator(s) or the principal investigator(s). The representative for the coordinating investigator (s) or the principal investigator(s) will have the responsibility to review the final study results to confirm to the best of his/her knowledge it accurately describes the conduct and results of the study. The representative for coordinating investigator(s) or the principal investigator(s) will be selected from the participating investigators by the sponsor prior to database lock.

## **12.2 Procedure for Clinical Study Quality Control**

### **12.2.1 Clinical Study Monitoring**

The sponsor or delegated CRO is responsible for monitoring the clinical study to ensure that subject's human rights, safety, and well-being are protected, that the study is properly conducted in adherence to the current protocol and GCP, and study data reported by the investigator/sub-investigator are accurate and complete and that they are verifiable with study-related records such as source documents. The sponsor is responsible for assigning study monitor(s) to this study for proper monitoring. They will monitor the study in accordance with planned monitoring procedures.

- CONFIDENTIAL -

### **12.2.2 Direct Access to Source Data/Documents**

The investigator and the study site must accept monitoring and auditing by the sponsor or delegated CRO as well as inspections from the IRB/IEC and relevant regulatory authorities. In these instances, they must provide all study-related records including source documents when they are requested by the sponsor monitors and auditors, the IRB/IEC, or regulatory authorities. The confidentiality of the subject's identities shall be well protected consistent with local and national regulations when the source documents are subject to direct access.

### **12.2.3 Data Management**

Data Management will be coordinated by the Data Management Team of the sponsor in accordance with the SOPs for data management. All study-specific processes and definitions will be documented by Data Management. eCRF completion will be described in the eCRF instructions. Coding of medical terms and medications will be performed using MedDRA and World Health Organization (WHO) Drug Dictionary, respectively.

### **12.2.4 Quality Assurance**

The sponsor is implementing and maintaining quality assurance and quality control systems with written SOPs to ensure that trials are conducted and data are generated, documented, recorded and reported in compliance with the protocol, GCP and applicable regulatory requirement(s).

The sponsor or sponsor's designee may arrange to audit the clinical study at any or all investigational sites and facilities. The audit may include on-site review of regulatory documents, CRFs, and source documents. Direct access to these documents will be required by the auditors.

## **12.3 Contraception Requirements**

### **CONTRACEPTION GUIDANCE FOR MALE PARTICIPANTS WITH PARTNER(S) OF CHILD BEARING POTENTIAL.**

A sexually active male subject with female partner(s) who is of childbearing potential is eligible if:

- Agrees to use a male condom starting at screening and continue throughout the study treatment and for at least 3 months after the last dose of study drug. If the male subject has not had a vasectomy or is not sterile at least 6 months prior to screening as defined below his female partner(s) is utilizing 1 form of highly effective birth control\* per locally accepted standards starting at screening and continue throughout study treatment and for at least 3 months after the male subject receives his last dose of study drug.a

\*Highly effective forms of birth control include:

- Consistent and correct usage of established hormonal contraceptives that inhibit ovulation,
- Established intrauterine device (IUD) or intrauterine hormone releasing system (IUS).

- CONFIDENTIAL -

- Bilateral tubal occlusion
- Vasectomy (A vasectomy is a highly effective contraception method provided the absence of sperm has been confirmed. If not, an additional highly effective method of contraception should be used)
- Male is sterile due to a bilateral orchiectomy or radical cystoprostatectomy/removal of seminal vesicles
- Sexual Abstinence is considered a highly effective method only if defined as refraining from heterosexual activity during the entire period of risk associated with the study drug. The reliability of sexual abstinence needs to be evaluated in relation to the duration of the study and the preferred and usual lifestyle of the participant

a Local laws and regulations may require use of alternative and/or additional contraception methods.

## **12.4 List of Excluded Concomitant Medications**

The following medications are prohibited within 4 weeks of day 1 and during the study treatment period:

- 5  $\alpha$ -reductase inhibitors (finasteride, dutasteride);
- Estrogens;
- Cyproterone acetate, megestrol acetate;
- Biologic or other agents with antitumor activity against prostate cancer (with the exception of those therapies identified in exclusion criterion No. 1);
- Systemic glucocorticoids greater than the equivalent of 10 mg/day of prednisone intended for the treatment of prostate cancer;
- Herbal medications with known hormonal antiprostate cancer activity and/or known to decrease PSA levels (i.e., saw palmetto);
- Androgens (testosterone, dehydroepiandrosterone, etc.);
- Investigational agents.

In addition, bisphosphonates and denosumab are prohibited unless stabilized for 2 weeks prior to randomization and held constant, as tolerated, throughout study treatment or administered for diagnosis of osteoporosis.

## **12.5 Liver Safety Monitoring and Assessment**

Any subject enrolled in a clinical study with active drug therapy and reveals an increase of serum aminotransferases to  $> 3 \times$  ULN (to  $> 5 \times$  ULN in subjects with liver metastases), or bilirubin  $> 2 \times$  ULN, should undergo detailed testing for liver enzymes (including at least ALT, AST, alkaline phosphatase, and TBL). Testing should be repeated within 48 to 72 hours of notification of the test results. Moderate or severe liver abnormality should inform the investigator, study monitor and study team. Subjects should be asked if they have any symptoms suggestive of hepatobiliary dysfunction.

- CONFIDENTIAL -

### **Definition of Liver Abnormalities**

Confirmed abnormalities will be characterized as moderate or severe where ULN:

	ALT or AST	TBL
Moderate	$> 3 \times \text{ULN}$ (in subjects without liver metastases), $> 5 \times \text{ULN}$ (in subjects with liver metastases)	or $> 2 \times \text{ULN}$
Severe*	$> 3 \times \text{ULN}$	and $> 2 \times \text{ULN}$

In addition, the subject should be considered to have severe hepatic abnormalities for any of the following:

- ALT or AST  $> 8 \times \text{ULN}$ ;
- ALT or AST  $> 5 \times \text{ULN}$  for more than 2 weeks (in the absence of liver metastases);
- ALT or AST  $> 3 \times \text{ULN}$  and INR  $> 1.5$  (If INR testing is applicable/evaluated);
- ALT or AST  $> 3 \times \text{ULN}$  with the appearance of fatigue, nausea, vomiting, right upper quadrant pain or tenderness, fever, rash and/or eosinophilia ( $> 5\%$ ).

The investigator may determine that abnormal liver function results, other than as described above, may qualify as moderate or severe abnormalities and require additional monitoring and follow-up.

### **Follow-up Procedures**

Confirmed moderate or severe abnormalities in hepatic functions should be thoroughly characterized by obtaining appropriate expert consultations, detailed pertinent history, physical examination and laboratory tests. The site should complete the liver abnormality case report form (LA-CRF) that has been developed globally and can be activated for any study, or appropriate document. Subjects with confirmed abnormal LFTs should be followed as described below.

Confirmed moderately abnormal LFTs should be repeated 2-3 times weekly then weekly or less if abnormalities stabilize or the study drug has been discontinued and the subject is asymptomatic.

Severe hepatic liver function abnormalities as defined above, in the absence of another etiology may be considered an important medical event and may be reported as an SAE. The Sponsor should be contacted and informed of all subjects for whom severe hepatic liver function abnormalities possibly attributable to study drug are observed.

To further assess abnormal hepatic laboratory findings, the investigator is expected to:

- Obtain a more detailed history of symptoms and prior or concurrent diseases. Symptoms and new onset-diseases should be recorded as 'AEs' on the AE page of eCRF. Illnesses and conditions such as hypotensive events, and decompensated cardiac disease that may lead to secondary liver abnormalities should be noted. Nonalcoholic steatohepatitis (NASH) is seen in obese hyperlipoproteinemic, and/or diabetic subjects and may be

- CONFIDENTIAL -

associated with fluctuating aminotransferase levels. The investigator should ensure that the medical history form captures any illness that predates study enrollment that may be relevant in assessing hepatic function.

- Obtain a history of concomitant drug use (including nonprescription medication, complementary and alternative medications), alcohol use, recreational drug use and special diets. Medications, including dose, should be entered on the concomitant medication page of the eCRF. Information on alcohol, other substance use and diet should be entered on the LA-CRF or an appropriate document.
- Obtain a history of exposure to environmental chemical agents.
- Based on the subject's history, other testing may be appropriate including:
  - acute viral hepatitis (A, B, C, D, E or other infectious agents).
  - ultrasound or other imaging to assess biliary tract disease
  - other laboratory tests including INR, direct bilirubin
- Consider gastroenterology or hepatology consultations.
- Submit results for any additional testing and possible etiology on the LA-CRF or an appropriate document.

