### **5.5.1.2 Potential Cases of Drug-Induced Liver Injury**

Refer to [\[Appendix 12.5 Liver Safety Monitoring and Assessment\]](#) for detailed instructions on Drug Induced Liver Injury (DILI). Abnormal values in aspartate transaminase (AST) and/or alanine transaminase (ALT) concurrent or with abnormal elevations in total bilirubin that meet the criteria outlined in [\[Appendix 12.5 Liver Safety Monitoring and Assessment\]](#), in the absence of other causes of liver injury, are considered potential cases of drug-induced liver injury (potential Hy's Law cases) and are always to be considered important medical events and reported per [\[Section 5.5.5 Reporting of Serious Adverse Events\]](#).

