### 5.5.5 Reporting of Serious Adverse Events

The collection of AEs and the expedited reporting of SAEs will start following the signing of the informed consent for the double-blind period and will be collected until 30 days after the last dose of study drug (including the double-blind period and open-label phase if applicable), or initiation of a new therapy for prostate cancer, or the subject is determined to be a screen failure, whichever occurs first. During the post treatment follow-up period, only symptomatic skeletal events need to be reported.

In the case of a SAE, the investigator must contact the sponsor by fax or email immediately (within 24 hours of awareness). The investigator must complete and submit an SAE Worksheet containing all information that is required by local and /or regional regulations to the sponsor by email or fax immediately (within 24 hours of awareness).

The SAE worksheet must be signed by a medically qualified investigator (as identified on Delegation of Authority Log). Signature confirms accuracy and completeness of the SAE data as well as the investigator causality assessment including the explanation for the causality assessment.

If the SAE is associated with emergency unblinding as outlined in [\[Section 4.4.4 Breaking the treatment code for Emergency\]](#) this is to be recorded on the SAE worksheet. Within the SAE worksheet, the investigator is to include when unblinding took place in association with the SAE.

For contact details, see [\[Section II Contact Details of Key Sponsor's Personnel\]](#). Fax or email the SAE/Special Situations Worksheet to:

Astellas Pharma Global Development Inc.

Pharmacovigilance

North America [contact]

North America alternate [contact]

- CONFIDENTIAL -

International [contact]

Email: [contact]

Copy: acn\[contact]

If there are any questions, or if clarification is needed regarding the SAE, contact the sponsor's Medical Monitor or his/her designee (see [[Section II Contact Details of Key Sponsor's Personnel](#)]).

Follow-up information for the event should be sent promptly (within 7 days of the initial notification).

Full details of the SAE should be recorded on the medical records, SAE/Special Situation Worksheet and on the eCRF.

The following minimum information is required:

- International study number (ISN)/Study number
- Subject number, sex and age
- The date of report
- A description of the SAE (event, seriousness of the event)

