### **Study Discontinuation**

In the absence of an explanation for increased LFTs, such as viral hepatitis, preexisting or acute liver disease, presence of liver metastases, or exposure to other agents associated with liver injury, the subject may be discontinued from the study. The investigator may determine that it is not in the subject's best interest to continue study enrollment. Discontinuation of treatment should be considered if:

- ALT or AST  $> 8 \times$  ULN;
- ALT or AST  $> 5 \times$  ULN for more than 2 weeks (in subjects without liver metastases);
- ALT or AST  $> 3 \times$  ULN and TBL  $> 2 \times$  ULN or INR  $> 1.5$  (If INR testing is applicable/evaluated);
- ALT or AST  $> 5 \times$  ULN and (TBL  $> 2 \times$  ULN in subjects with liver metastases);
- ALT or AST  $> 3 \times$  ULN with the appearance of fatigue, nausea, vomiting, right upper quadrant pain or tenderness, fever, rash and/or eosinophilia ( $> 5\%$ ).

In addition, if close monitoring for a subject with moderate or severe hepatic laboratory tests is not possible, drug should be discontinued.

\*Hy's Law Definition-Drug-induced jaundice caused by hepatocellular injury, without a significant obstructive component, has a high rate of bad outcomes, from 10–50% mortality (or transplant). The 2 “requirements” for Hy's Law are: 1. Evidence that a drug can cause hepatocellular-type injury, generally shown by an increase in transaminase elevations higher than 3 times the ULN (“ $2 \times$  ULN elevations are too common in treated and untreated subjects

- CONFIDENTIAL -

to be discriminating”). 2. Cases of increased bilirubin (at least  $2 \times$  ULN) with concurrent transaminase elevations at least  $3 \times$  ULN and no evidence of intra- or extra-hepatic bilirubin obstruction (elevated alkaline phosphatase) or Gilbert’s syndrome [[Temple, 2006](#)].

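### Protocol 5.5.1.2 makes 24-hour SAE reporting of potential Hy's Law cases mandatory, but Appendix 12.5 words it as optional and asks only for untimed sponsor notification

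*Protocol*

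**What the plan says.** Protocol 5.5.1.2 (Potential Cases of Drug-Induced Liver Injury) refers the site to Appendix 12.5 for detailed instructions. It covers AST and/or ALT abnormalities accompanied by bilirubin elevations that meet the appendix criteria, where nothing else explains the liver injury. Such cases "are always to be considered important medical events and reported per" section 5.5.5. Section 5.5.5 requires contact with the sponsor, and an SAE worksheet, within 24 hours of awareness.

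Appendix 12.5 defines the severe class under Definition of Liver Abnormalities. The table row is ALT or AST > 3 x ULN together with TBL > 2 x ULN. Its asterisk leads to the note at the end of the appendix that begins "Hy's Law Definition-Drug-induced jaundice caused by hepatocellular injury". Further criteria are then added: "the subject should be considered to have severe hepatic abnormalities for any of the following", with four items listed.

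Under Follow-up Procedures the appendix states that severe abnormalities, as defined above and with no other etiology, "may be considered an important medical event and may be reported as an SAE". The next sentence reads: "The Sponsor should be contacted and informed of all subjects for whom severe hepatic liver function abnormalities possibly attributable to study drug are observed". The same section asks the site to complete a liver abnormality form or an appropriate document.

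**The concern.** Section 5.5.1.2 removes investigator discretion for a defined set of liver cases, and the appendix it points to gives that discretion back. This matters because of how seriousness is decided in section 5.5.2. A patient who is not hospitalised, disabled or in immediate danger qualifies as an SAE only through the category of medically important events, which otherwise rests on judgment. For these patients, the choice between *always* and *may* decides whether an SAE is filed.

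Several things follow from SAE status: the 24-hour report, the sponsor's assessment for expedited reporting (5.5.5), possible code-breaking by the sponsor if the case is a SUSAR (4.4.5), and entry in the serious-TEAE tables by arm (SAP 7.5.1). The list of common SAEs in Appendix 12.6, whose single occurrences may be left out of expedited reporting, contains no hepatic event. Once filed, these cases could not be set aside on that ground.

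**Working it through.** No figure in the plan depends on this point and no arithmetic applies. The check is a comparison of the two passages.

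| Question | Protocol 5.5.1.2 | Protocol Appendix 12.5 |
|---|---|---|
| Which cases? | AST and/or ALT with raised bilirubin, meeting the 12.5 criteria | All severe abnormalities: ALT or AST > 3 x ULN with TBL > 2 x ULN, plus four other criteria |
| Other cause? | Must be absent | Must be absent |
| Important medical event? | Always | May be |
| SAE report? | Yes, per 5.5.5, within 24 hours | May be |
| Exception for Hy's Law cases? | Not needed | None stated |
| Sponsor informed? | Through the SAE report | Should be, if possibly attributable to study drug; no time limit |

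1. **Overlap.** The appendix class is wider than that of 5.5.1.2, but it contains the aminotransferase-plus-bilirubin row, and that row is footnoted to Hy's Law. These cases fall under both rules.
2. **Does a condition explain the difference?** No. Both passages require that no other cause be present.
3. **Does the cross-reference resolve it?** No. Section 5.5.1.2 sends the reader to the appendix, where the weaker wording stands. The appendix passage does not refer back to 5.5.1.2 or 5.5.5.
4. **Do other routes restore the 24-hour SAE report?**
   - The sponsor notice in 12.5 is a *should*, is untimed, does not invoke 5.5.5, and is limited to cases judged possibly attributable to study drug.
   - The liver abnormality form is also a *should*, and another document may replace it.
   - Section 5.5.1.1 requires clinically significant abnormal results unrelated to underlying disease to be reported as an AE or SAE. It depends on investigator judgment and does not settle seriousness.
   - Liver tests are run at each site; only PSA goes to the central laboratory (5.4.2). Site data should be entered within 5 days of the visit (8.1). The documents describe no central-laboratory alert for liver values.
5. **Which analyses are touched?** The serious-TEAE summaries in SAP 7.5.1 depend on an SAE having been filed. SAP 7.5.2.1 does not. It counts patients by treatment group with ALT and/or AST > 3 x ULN and total bilirubin > 2 x ULN, and the same with alkaline phosphatase < 2 x ULN, from laboratory values.

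**The case against.** The strongest reply is that both passages can be obeyed at once. A permissive sentence over a broad class does not forbid reporting, and a site is bound by the body of the protocol as well as its appendix. On this view *may* was meant for the four other severe criteria and *always* for the Hy's Law subset. A site that reports every such case does satisfy both passages. But the appendix sentence covers everything defined above it and makes no such distinction. A site that does not report also satisfies the appendix, while breaching 5.5.1.2.

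A reader might also infer three stronger things that the documents do not support:

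- **That these cases can go unreported altogether.** Appendix 12.5 asks that the sponsor be told of severe cases possibly attributable to study drug and that a liver form or equivalent be completed. Protocol 7.5.2 has clinically significant laboratory abnormalities recorded as AEs. Under 5.5.2 the sponsor, once informed, can itself judge an event serious. What can be lost is the 24-hour SAE report.
- **That the two rules cover the same patients.** They overlap. The appendix also takes in ALT or AST > 8 x ULN, > 5 x ULN for more than 2 weeks, > 3 x ULN with INR > 1.5, and > 3 x ULN with symptoms, rash or eosinophilia.
- **That the blinded comparison of liver safety is compromised.** SAP 7.5.2.1 makes that comparison from laboratory data, and chemistry is scheduled at every treatment visit.

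It is also fair to note that Protocol 1.2.1 reports no evidence of hepatotoxicity with enzalutamide in animals or in the clinical program, which suggests that few cases would arise.

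**Conclusion.** The contradiction is real and can be read directly from the text. For cases with ALT or AST > 3 x ULN, TBL > 2 x ULN and no other cause, one section makes SAE reporting mandatory and the appendix it cites makes it optional. A site following the appendix could inform the sponsor without filing a 24-hour SAE report. The consequence is limited to the timing of expedited reporting and the completeness of SAE counts. The laboratory comparison by arm and all efficacy endpoints are untouched.

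The number of affected patients cannot be derived, because the documents give no expected rate for such cases among the approximately 180 subjects. Few cases would be expected, but each is a potential expedited report, and the appendix's own note cites 10–50% mortality or transplant for injury of this kind. The conclusion assumes that some sites would take the appendix at its word, which is plausible because 5.5.1.2 directs them there. This is an internal inconsistency, not a design choice, and it is worth correcting on safety-reporting grounds.

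**What to change.** Reconcile 5.5.1.2 and Appendix 12.5 so that a single reporting rule applies to cases meeting the aminotransferase-plus-bilirubin criteria without another cause. One way is to replace the permissive wording in Follow-up Procedures, for those cases, with a cross-reference to 5.5.1.2 and 5.5.5. State separately which reporting rule applies to the other severe categories, and whether the sponsor notification has a time limit.

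The cost is one or two sentences in an appendix and a short note to sites. It needs no new data collection, no change to the SAP and no change to any treatment rule.
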